## **Aim 2**

Aim 2 is to investigate factors which affect response to treatment.

Hypothesis 2a. Baseline cognitive ability, depression, sleep, and presence of PTSD will have a significant effect on response to treatment.

**Analysis Plan for Hypotheses 2a.** To test the second specific aim, a general linear regression will be used to determine whether any of the four factors is associated with response to treatment. The analysis will be restricted to the participants assigned to the intervention group. The dependent variable for the regression model will be 'time to completion' on the TOL, and the independent variables will be CWI, BDI-II, and PCL-M scores.

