### **Aim 2**

Aim 2 is to investigate factors which affect response to treatment.

Hypothesis 2. Baseline cognitive ability, depression, sleep, and presence of PTSD will have a significant effect on response to treatment.

Analysis Plan for Hypotheses 2. To test the second specific aim, a general linear regression will be used to determine whether any of the four factors is associated with response to treatment. The analysis will be restricted to the participants assigned to the intervention group. The dependent variable for the regression model will be 'time to completion' on the TOL, and the independent variables will be CWI, BDI-II, PCL-M and PSQI scores.

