Primary Outcome Measure: Tower of London (TOL): is a computerized program in which patients are shown two pictures simultaneously of a goal board and a test board (Unterrainer et al, 2006). Each picture shows three balls of different colors arranged on three pegs, with the balls in a unique arrangement in each picture. Patients are instructed to determine the fewest possible moves of the balls in the test picture to make the

arrangement of balls identical to that of the goal picture within 60 seconds. The screen reports whether the response is correct or incorrect. Test administration is less than 45 minutes for each session (pre/post/follow-up). Each set consists of 70 problems of variable difficulty, determined by variables, such as, the number of moves needed to solve the problem (Berg and Byrd, 2002). In turn, each set consists of the same number of 4, 5, 6 or 7 move problems and has the same average difficulty level. Difficulty rating is based on global and specific problem parameters shown to affect the planning process (Kaller, 2007, 2008, 2009; Berg, Byrd, McNamara, & Case, 2010; Kaller, Unterrainer, Rahm, & Halsband, 2004). The dependent variables are the total time spent solving the problem and the optimal moves made toward the goal display.

Based on our previous studies, executive function represents three factors (behavior regulation, emotional regulation and metacognition) (Waid, Wen, Heaton, andVELOZO, submitted to Neuropsychology). GMT is a metacognitive training with emphasis on planning prior to engaging in a complex task. Therefore, a primary measure that captures the planning and problem solving of a multi-step task, called the Tower of London (TOL), was selected. Based on results from our preliminary study, the dependent variables of total time and optimal moves will be used to determine treatment effect. While, not all of the participants in our previous work demonstrated significant improvement on these variables, group differences based on paired T-tests were significant in Total Time ( $p=0.026$ ) and Optimal Moves ( $p=0.022$ ) from baseline to treatment. In addition to our findings, Levine (2011) demonstrated a significant change in the TOL following GMT for a mixed neurological sample compared to a control group. Thus, the TOL appears to be sensitive to the effects of GMT.

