#### Measures for Secondary Analysis

Beck Depression Inventory (BDI): is a 21-item questionnaire filled out by the individual diagnosed with TBI in the presence of the Principal Investigator. Questions are rated using a 4-point scale and cover symptoms of depression such as hopelessness, irritability, guilt, fatigue, weight loss and lack of interest in sex. The reliability of the BDI in TBI has been reported at .92 (Green, 2001; Beck et al, 1996).

Post-Traumatic Stress Disorder (PTSD) symptom checklist-military (PCL-M): The checklist is a 17-item self-report measure of the 17 DSM-IV symptoms of PTSD with a 5-point rating scale ranging from rarely to extremely frequent. The range of total score is 17 to 85. Internal consistency for the overall scale is .95 with cross validation to clinician-administered interviews ranging from .64 for Vietnam veterans to .83 for motor vehicle accident and assault victims (Weathers, 1991 & 1993; Blanchard et al, 1996). The PCL-M will be used to determine the impact of PTSD on the response to treatment.

Pittsburgh Sleep Quality Index (PSQI): is a 19-item self-rated questionnaire for evaluating subjective sleep quality over the previous month. Seven component scores are added to obtain a global score ranging from 0–21, with higher scores indicating worse sleep quality. The PSQI has a sensitivity of 89.6% and specificity of 86.5% for identifying cases with sleep disorder and has been used in a wide range of population-based and clinical studies. Since sleep disturbances are common complaints for Veterans returning from deployment and has been known to impair cognition, the PSQI will be used to determine whether sleep disturbances interfere with treatment response.

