Repeatable Battery for the Assessment of Neuropsychological Status (RBANS): is a cognitive screening instrument The RBANS is composed of 12 subtests that yield 5 index scores and a total score. The subtests of List Learning and Story Memory comprise the Immediate Memory Index; Figure Copy and Line Orientation yield the Visuospatial/Constructional Index; Picture Naming and Semantic Fluency yield the Language Index; and Digit Span and Coding comprise the Attention Index. Four subtests make up the Delayed Memory Index, specifically, List Recall, List Recognition, Story Recall, and Figure Recall (Randolph, Tierney, Mohr, & Chase, 1998). Administration is approximately 20 minutes and has been used to assess cognition in mTBI (Cooper et al., 2010). The index scores of the RBANS will be used to characterize the patient's cognitive capacity and to determine whether particular aspects of cognitive ability impact response to treatment.

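### The SAP's Aim 2 regression promises to test four factors but lists three predictors: sleep (PSQI) is missing, so the sleep hypothesis goes untested as written

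*Combined protocol and SAP*

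**What the plan says.** Section 7, Aim 2 puts forward the hypothesis "Baseline cognitive ability, depression, sleep, and presence of PTSD will have a significant effect on response to treatment". A general linear regression is then to determine "whether any of the four factors is associated with response to treatment". The population is fixed: "The analysis will be restricted to the participants assigned to the intervention group". The model is given as "time to completion' on the TOL, and the independent variables will be CWI, BDI-II, and PCL-M scores".

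Section 5 (Specific Aims, Aim 2) describes the same hypothesis, population and outcome, but there "the independent variables will be CWI, BDI-II, PCL-M and PSQI scores". Section 6 (Measures for Secondary Analysis) gives the reason for collecting the sleep scale: "the PSQI will be used to determine whether sleep disturbances interfere with treatment response". Table 1 schedules the PSQI before treatment, after treatment and at one month.

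In both versions the dependent variable is TOL completion time, with no visit, change score or baseline adjustment named. Section 6 has the TOL administered before treatment, after treatment and at follow-up. Aim 1, by contrast, compares the arms on improvement in TOL time.

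**The concern.** Section 7 is the statistical analysis plan, and nothing in the document says which section governs if the two differ. An analyst who follows its predictor list leaves one of the four hypothesised factors out. An analyst who notices the mismatch must choose a model, and if that happens after the data are seen, the choice is post hoc.

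Omission also affects the factors that stay in. Sleep, depression and PTSD scores may well be correlated. If sleep carries the association, part of it is then credited to whichever correlated score remains in the model.

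Two details of the same paragraph deserve attention in the same edit. Taken literally, the outcome is a level of performance, not a response. And because only the GMT arm is analysed, an association with change cannot be separated from practice gain or recovery that might occur in either arm.

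**Working it through.** **1. Count of factors against predictors.** The plan's own figure is four. Matching CWI to cognitive ability follows by elimination, since the other three scales are described by what they measure.

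| Factor in hypothesis | Measure | Section 5 list | Section 7 list |
|---|---|---|---|
| Cognitive ability | CWI | yes | yes |
| Depression | BDI-II | yes | yes |
| PTSD | PCL-M | yes | yes |
| Sleep | PSQI | yes | **no** |
| Total | | 4 | 3 |

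Section 5 reproduces the stated four; section 7 does not. This step needs no assumption.

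**2. Inputs for size.** The GMT arm of 38 comes from section 6, Table 2. The documents give no correlations for Aim 2, so all of those below are assumed: predictors standardised with common correlation ρ of 0, 0.3 or 0.5, and two-sided tests at 5%. Simulated rates for steps 3 to 5 use 20,000 trials per setting.

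**3. False flags when PSQI is left out.** Let sleep S be the only true predictor: Y = 0.4·S + √(1 − 0.4²)·e. With S omitted, each of the other three takes an expected slope of 0.4·ρ/(1 + 2ρ):
- ρ = 0: 0
- ρ = 0.3: 0.12/1.6 = 0.075
- ρ = 0.5: 0.20/2 = 0.100

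Proportion of trials in which at least one of CWI, BDI-II and PCL-M is significant (n = 38):

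| ρ | PSQI omitted | PSQI included | Excess |
|---|---|---|---|
| 0 | 14% | 14% | none |
| 0.3 | 19.3% | 13.6% | 5.7 points |
| 0.5 | 21.0% | 13.1% | 7.9 points |

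The rate with PSQI included is roughly what three independent 5% tests give: 1 − 0.95³ = 14.3%. It is not itself caused by the omission.

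**4. What is lost for sleep.** As listed, sleep cannot be flagged at all. With PSQI in the model and n = 38, a sleep-change correlation of 0.2 / 0.3 / 0.4 would be detected in 15-21% / 29-43% / 50-69% of trials (ρ from 0.5 down to 0). With 30 analysed, an assumed figure after the section 7 exclusions, this falls to 12-17% / 23-34% / 39-57%.

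**5. Cost of restoring PSQI.** Residual degrees of freedom are n − k − 1: 38 − 3 − 1 = 34 becomes 38 − 4 − 1 = 33. The smallest partial R² detectable with 80% power is about 0.18 in both cases. Power for another factor falls by about 1 to 4 points: for example 44% to 43% (r = 0.3, ρ = 0), or 53% to 49% (r = 0.4, ρ = 0.5).

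**6. Level against change.** Write pre = L + e₁ and post = L + e₂ + constant, with L the stable TOL level, and let a factor x be linked only to L. Then cov(x, post) = cov(x, L), which is not zero, while cov(x, post − pre) = 0. As an illustration, take x correlated 0.4 with L and a pre-post correlation of 1/(1 + 0.65²) = 0.70. With n = 38 and 4,000 runs, x is flagged in about 53% of trials if post-treatment time is the outcome, against about 5% if change is.

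**The case against.** The best defence is that this is a drafting slip which the document itself largely resolves. The section 7 hypothesis names sleep, the next sentence counts four factors, section 5 gives the full list, section 6 states the purpose of the scale, and Table 1 schedules it. A careful analyst would probably include it. That stands as an account of how the omission arose, and it makes the repair easy. It does not make the section 7 list correct, and no rule of precedence settles the conflict.

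A reader might infer that sleep was deliberately dropped from the aim. The text does not support that: section 7 still hypothesises sleep and still counts four factors.

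A reader might also infer that the one-arm model is offered as a test of whether these factors modify the GMT effect. The aim and hypothesis do use causal wording, but the analysis sentence speaks only of association, the restriction to the intervention arm is declared, and a two-arm interaction for PTSD severity is planned separately under Aim 1. So the one-arm point is about labelling, not an invalid analysis.

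On the outcome, change is the natural reading of response to treatment; only the explicit definition is missing.

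Finally, 38 is not a settled number. Section 6 also anticipates 168 enrolled over both sites, and section 4 speaks of recruiting 40. A larger GMT arm would raise the power to detect sleep. It would not remove the false flags: the slopes in step 3 do not depend on n, so with more participants they would be detected more often.

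**Conclusion.** The contradiction is established from the text alone: section 7 promises four factors and lists three, while section 5 lists four for the same model. As written, the sleep hypothesis is untested.

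The effect on the remaining factors is modest and conditional. It is an excess of about 6 to 8 percentage points in the chance of flagging at least one of them, if sleep is the only true predictor at r = 0.4, n is 38 and predictors correlate 0.3-0.5. It is nil if they are uncorrelated. All these rates rest on assumed correlations and are illustrative. Possible range restriction of CWI by the eligibility rule is ignored.

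The undefined outcome and the one-arm label are lesser points of wording in the same paragraph. The matter should be fixed, but it concerns the secondary aim only. Nobody should infer a problem for the primary result: the Aim 1 two-sample t-test does not use this model.

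**What to change.** In section 7, Aim 2:

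1. Restore PSQI to the predictor list, so that it reads CWI, BDI-II, PCL-M and PSQI and agrees with section 5.
2. Define the dependent variable as pre- to post-treatment change in TOL completion time, in line with the improvement compared in Aim 1. Make the same change in section 5, which has the same gap.
3. State that results will be reported as predictors of change within the GMT arm, in keeping with the plan's own language of association.

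All three are wording changes, best made before outcome data are examined. The pre-treatment PSQI and the TOL at each visit are already in the testing schedule, so no new data are needed. The statistical cost is the one degree of freedom and the 1 to 4 points of power shown above.

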## **8. Possible Discomforts and Risks:**

The potential risks are minimal for the proposed intervention (group therapy). The standard of care for Veterans with mTBI is to receive cognitive therapy in group or individual settings. The risks of the proposed research would not increase from the current risks that patients experience in traditional therapy.

Patients may become anxious when discussing the trauma, they experienced and the deficits they continue to face on a daily basis. Fatigue and/or anxiety may occur while performing screening tests and tests prior to each session. Subjects with attention and concentration deficits may have difficulty completing the testing within one session. The PI will monitor patient anxiety and recommend alternative therapies such as individual speech therapy and additional psychological services that are available to the patient.

## **9. Possible Benefits:**

The proposed therapy has the potential to improve the subject's ability to organize and complete tasks by utilizing a strategy that can be used in various settings. The group therapy process also will provide peer support to help cope with the frustration of living with executive dysfunction. A group therapy also allows for more than one subject to receive therapy during the same time frame.

## **9. Conflict of Interest:**

None of the investigators have a conflict of interest in any part of this study.
